5.1. Synopsis

Methodology:	
Clinical and Safety Evaluations will be performed at:
 
 1. Visit 1/Screening 2. Visit 2/Baseline, Day 1 3. Visit 3/Week 2, Day 15 (\pm 3 Days) 4. Visit 4/Week 4, Day 29 (\pm 3 Days) 5. Visit 5/Week 8, Day 57 (\pm 3 Days) 6. Visit 6/Week 12, Day 85 (\pm 4 Days)/End of Treatment/End of Study) 
Patients will be admitted into the study after all inclusion/exclusion criteria have been met, including a clinical diagnosis of rosacea and after written informed consent has been obtained. Subjects with severe rosacea who are appropriate for systemic treatment need to be counseled regarding their treatment options by the Principal Investigator.
 
At each visit, a 5-point IGA scale of rosacea; rosacea erythema, and telangiectasia; and inflammatory (papules, pustules) lesion counts will be performed and recorded.
 
Safety will be assessed at all visits, and will include monitoring of local adverse experiences, Investigator Cutaneous Safety Assessment rating of dryness and scaling and Local Tolerability Assessment rating of itching and burning/stinging on a scale ranging from 0 (None) to 3 (Severe); patients will complete a Patient Reported Outcomes (PRO) questionnaire at Visit 2, 3, 4, 5 and 6 and Rosacea Quality of Life Questionnaire (RosaQoL) at Baseline and Visit 6 or at early termination..
 
Standardized photography of facial rosacea at Visit 2, 3, 4, 5 and 6 will be performed at select site(s).
 
In addition to IGA, at each visit, the following safety measures will be recorded: monitoring for any AE including local and systemic; investigator Cutaneous Safety Assessment rating of erythema, dryness and scaling and Local Tolerability Assessments rating of itching and burning/stinging on a scale ranging from 0 (None) to 3 (Severe).
 
Urine pregnancy tests will be performed on females of child-bearing potential at Screening, Baseline and every 4 weeks during study or at early termination.
 
Regardless of the duration of the study, patients that exhibit serious adverse event (SAE), will be followed up until the SAE resolves, based on investigator's medical judgment.

Clinical Trial Duration	
Screening: -35 to 0 days prior to Baseline
 
Duration of treatment: 12 weeks/84 days
 
Patients have the right to stop the study for any reason at any given time.

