5.2. Study Flow Chart

Procedures	Visit 1 ¹	Visit 2 ²	Visit 3 ²	Visit 4 ²	Visit 5 ²	Visit 6 ^{2,3} (EOT ⁴ / EOS ⁵)
Name of Visit	Screening -35 – 0	Baseline Day 1	Week 2 Day 15	Week 4 Day 29	Week 8 Day 57	Week 12 Day 85
Visit window			± 3 days	± 3 days	± 3 days	± 4 days
Informed Consent	X					
Demographics	X					
Medical History/Previous Therapies	X	X				
Brief Physical Examination		X				X
Inclusion/Exclusion Criteria	X	X				
Urine Pregnancy Test ⁶	X	X		X	X	X
IGA	X	X	X	X	X	X
Inflammatory Lesion Counts	X	X	X	X	X	X
Assessment of Eligibility		X				
Rosacea Erythema Assessment		X	X	X	X	X
Telangiectasia Assessment		X	X	X	X	X
Randomization		X				
Cutaneous Safety Assessment and Local Tolerability Assessments		X	X	X	X	X
Administer/ Review Patient Instructions		X	X	X	X	
Weigh Study Product		X		X	X	X
Study Product Dispensed		X ⁷		X	X	
Provide Cleanser and Moisturizer/Sunscreen ⁸		X				
Diary Card dispensed		X		X	X	
Study Product Collected				X	X	X
Diary Card collected				X	X	X
Patient Compliance Reviewed (Diary)			X	X	X	X
Concomitant Therapy and Medication History Reviewed	X	X	X	X	X	X
Adverse Events	X ⁹	X	X	X	X	X
Photography (select site(s))		X	X	X	X	X
Complete PAPSS, PAPI and PGI-S ^{10,11}		X	X	X	X	X
Complete PGI-C, PGI-TS and PGI-SE ¹²			X	X	X	X
Complete RosaQoL ¹³		X				X

¹ If no washout is needed, Visits 1 and 2 may occur on the same day. If a washout is needed, Visit 2 must occur within one month 35 days of Visit 1.

² All visit dates are in reference to Baseline, e.g., Visit 5 occurs 8 weeks ± 3 days after Baseline Visit.

³ All Week 12 procedures should be completed for Patients who terminate early.

⁴ EOT – end of treatment

⁵ EOS – end of study

⁶ All women of childbearing potential

⁷ Dispense one pump of test material at the Baseline Visit and dispense additional pump at Visit 4 and 5.

⁸ Or study approved cleanser and moisturizer

⁹ Adverse events after ICF is signed will be collected.

¹⁰ PAPSS is Patient Assessment of Papulopustular rosacea Signs and Symptoms; PAPI is Patient Assessment of Papulopustular rosacea Impacts; PGI-S is Patient Global Impression of Symptom Severity. Questionnaires will be completed prior to PI assessment.

¹¹ In case Screening Visit and Baseline are on the same day, the PRO questionnaires should be completed prior to screening procedures.

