17.2. Definitions

An adverse event (AE) is defined as any untoward medical occurrence in a patient administered a medicinal product and which does not necessarily have to have a causal relationship with this treatment. An adverse event can therefore be any unfavorable and unintended sign, symptom, or disease temporally associated with the use of a medicinal product, whether or not considered related to this medicinal product.

A serious adverse event (SAE) is an adverse event that results in any of the following outcomes:

- Death
- Life-threatening event (i.e., the patient was, in the opinion of the investigator, at immediate risk of death from the event as it occurred. It does not include an event that, had it occurred in a more severe form, might have caused death)
- Requires in-patient hospitalization or prolongs hospitalization
- A persistent or significant disability/incapacity or substantial disruption of the ability to conduct normal life functions
- Congenital anomaly/birth defect
- Other adverse events that may be considered serious based upon appropriate medical judgment, may jeopardize the patient and may require medical or surgical intervention to prevent one of the outcomes listed above.

Immediately Reportable Adverse Events (IRAE) is any serious AE or any AE that necessitates discontinuation of study product, including pregnancy.

Unexpected Adverse Event is any adverse drug experience, the specificity or severity of which is not consistent with the current approved product labeling (package insert) for the study product, the Investigator's Brochure, or as described in the clinical protocol and consent materials.

Intensity of Adverse Events are the maximum intensity of an AE during a day should be recorded on the eCRF. If the intensity of an AE changes over a number of days, then separate entries should be made having distinct onset dates for the changes in severity.

- Mild - AEs are usually transient, requiring no special treatment, and do not interfere with patient's daily activities.
- Moderate - AEs typically introduce a low level of inconvenience or concern to the patient and may interfere with daily activities, but are usually ameliorated by simple therapeutic measures.
- Severe - AEs interrupt a patient's usual daily activity and traditionally require systemic drug therapy or other treatment.

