17.4. Eliciting and Reporting of Adverse Events

The investigator will periodically assess patients for the occurrence of adverse events. In order to avoid bias in eliciting adverse events, the patient or parent/legally authorized representative should be asked a non-specific question (e.g., "How have you been feeling since your last visit?") to assess whether any AE has been experienced since the last visit. All adverse events (as defined in [Section 17.2](#)), either observed by the Investigator or one of his/her medical collaborators, or reported by the patient spontaneously, or in response to direct questioning, will be reported and documented in the source and the study reporting forms. When reporting an adverse event, the Investigator must assign a severity grade to each event and declare an opinion on the relatedness of the event to the study product or procedure. Serious or unexpected adverse events must be reported to the CRO within 24 hours of when the Investigator first learns of the occurrence of the event.

Adverse events will be documented in the source document and recorded in a timely manner on case report forms. Adverse events that are identified at the last assessment visit (or the Early Termination Visit) must be recorded on the AE eCRF with the status of the AE noted.

Adverse event reporting begins from the signing of informed consent/assent. Study product-related adverse events should be followed until resolved or 30 days after the final study treatment. Regardless the duration of the study, patients that exhibit serious adverse event (SAE), will be followed up until the SAE resolves, based on investigator's medical judgment or are considered to be chronic (stabilized for at least 30 days). All events that are ongoing at this time will be recorded as ongoing on the eCRF.

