8.8.2 Adverse Events (AEs)

All AEs occurring during the study will be recorded and classified on the basis of MedDRA terminology. Descriptions of AEs will include the date of onset, the date the AE ended, the severity of the AE, the relationship to study product, the action taken regarding study product usage, the action taken to treat the AE, and the outcome. All reported treatment-emergent AEs (TEAEs) will be summarized by the number of patients reporting AEs, system organ class, severity, seriousness, and relationship to study product. TEAEs are those AEs with an onset on or after the date of the first study product application; if the AE is not indicated as prior to first application on the CRF then it will be considered a TEAE.

AEs will be summarized by treatment group and severity. Each patient will be counted only once within a system organ class or a preferred term by using the AEs with the highest severity within each category.

AEs will be summarized by treatment group and relationship to study product. Each patient will be counted only once within a system organ class or a preferred term by using the AEs with the greatest relationship within each category.

If relationship to study drug is reported as definitely, probably, or possible, then this is defined as related. If relationship to study drug is reported as unlikely or not related, then this is defined as unrelated.

Comparisons among treatment groups will be made by tabulating the frequency of patients with one or more AEs (classified into MedDRA terms) during the study. The Fisher's Exact test will be used to compare the proportion of patients in each treatment group who report any AE at a

significance level of 0.05. The specific system organ classes and preferred terms analyzed will be those that are reported by at least one percent of the patients in any treatment group.

All information pertaining to AEs noted during the study will be listed by patient, detailing verbatim given by the investigator, preferred term, system organ class, start date, stop date, severity, actions taken, and drug relatedness. The AE onset will also be shown relative (in number of days) to the day of initial application of the randomized study product.

Serious adverse events (SAEs) will be tabulated by patient within treatment groups.

In addition, a list of patients who discontinued from the study and a list of patients who experienced SAEs will also be provided.

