Week 8		
n	xx	xx
0 – None	xx (xx.x%)	xx (xx.x%)
1 – Mild	xx (xx.x%)	xx (xx.x%)
2 – Moderate	xx (xx.x%)	xx (xx.x%)
3 – Severe	xx (xx.x%)	xx (xx.x%)
Week 12		
n	xx	xx
0 – None	xx (xx.x%)	xx (xx.x%)
1 – Mild	xx (xx.x%)	xx (xx.x%)
2 – Moderate	xx (xx.x%)	xx (xx.x%)
3 – Severe	xx (xx.x%)	xx (xx.x%)

Note: No imputation of missing data.

SOURCE: USERNAME\SPONSOR\PROJECT\JOBNAME (DATE,TIME)

Table 14.3.1.2.1: Summary of Treatment-Emergent Adverse Event Characteristics
(Safety Population)
(Page 1 of 2)

	E-BPO 5% Cream (N=xxx)	Vehicle Cream (N=xxx)
Subjects Reporting Any Treatment-Emergent Adverse Event	xx (xx.x%)	xx (xx.x%)
Number of Treatment-Emergent Adverse Events	xx	xx
Subjects Reporting Any Serious Treatment-Emergent Adverse Event	xx (xx.x%)	xx (xx.x%)
Number of Serious Treatment-Emergent Adverse Events	xx	xx
Subjects Reporting Treatment-Emergent Adverse Event with Outcome of Fatal	xx (xx.x%)	xx (xx.x%)
Number of Treatment-Emergent Adverse Events with Outcome of Fatal	xx	xx
Subjects Who Discontinued Study Drug Due to a Treatment-Emergent Adverse Event	xx (xx.x%)	xx (xx.x%)
Number of Treatment-Emergent Adverse Events Leading to Discontinuation of Study Drug	xx	xx
Subjects Who Discontinued from the Study Due to a Treatment-Emergent Adverse Event	xx (xx.x%)	xx (xx.x%)
Number of Treatment-Emergent Adverse Events Leading to Discontinuation of Study	xx	xx

Note: Treatment-emergent adverse events are those events that were not indicated as occurring prior to first application.
Related defined as “Definitely”, “Probably”, or “Possible”. Not Related defined as “Unlikely” or “Not related”.

SOURCE: USERNAME\SPONSOR\PROJECT\JOBNAME (DATE, TIME)

Table 14.3.1.2.1: Summary of Treatment-Emergent Adverse Event Characteristics
(Safety Population)
(Page 2 of 2)

	E-BPO 5% Cream (N=xxx)	Vehicle Cream (N=xxx)
By Maximum Severity		
Severe	xx (xx.x%)	xx (xx.x%)
Moderate	xx (xx.x%)	xx (xx.x%)
Mild	xx (xx.x%)	xx (xx.x%)
By Strongest Relationship to Study Drug		
Related	xx (xx.x%)	xx (xx.x%)
Not Related	xx (xx.x%)	xx (xx.x%)
Maximum Severity within Relationship to Study Drug		
Related		
Severe	xx (xx.x%)	xx (xx.x%)
Moderate	xx (xx.x%)	xx (xx.x%)
Mild	xx (xx.x%)	xx (xx.x%)
Not Related		
Severe	xx (xx.x%)	xx (xx.x%)
Moderate	xx (xx.x%)	xx (xx.x%)
Mild	xx (xx.x%)	xx (xx.x%)

Note: Treatment-emergent adverse events are those events that were not indicated as occurring prior to first application.

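### With no rule to link the severity-change entries of one adverse event, TEAE event counts are inflated and an easing pre-treatment event can be classed as treatment-emergent

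*SAP*

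**What the plan says.** **Recording.** Protocol 17.2 says that when the intensity of an AE changes over a number of days, "separate entries should be made having distinct onset dates for the changes in severity". The direction of change is not restricted, so easing opens a new entry just as worsening does.

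**Collection before treatment.** Protocol 17.4 states that "Adverse event reporting begins from the signing of informed consent/assent", and footnote 9 of the flow chart in Protocol 5.2 agrees: "Adverse events after ICF is signed will be collected". The synopsis gives the window as "Screening: -35 to 0 days prior to Baseline". AEs that start before first application are therefore in the AE data.

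**Classification.** SAP 8.8.2 has two clauses in one sentence. The date clause is "TEAEs are those AEs with an onset on or after the date of the first study product application". The flag clause is "if the AE is not indicated as prior to first application on the CRF then it will be considered a TEAE". The footnotes to the TEAE tables in SAP Section 12 use the flag alone: "Treatment-emergent adverse events are those events that were not indicated as occurring prior to first application".

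**Outputs.** Table 14.3.1.2.1 has a row "Number of Treatment-Emergent Adverse Events", with parallel rows for serious TEAEs, fatal TEAEs and TEAEs leading to discontinuation. The SOC, PT, severity and relationship summaries count each patient once per category. Fisher's exact test is applied to proportions of patients, for SOCs and PTs reported by at least 1% of either arm.

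Neither document says how several entries of one event are joined, which onset date the joined event carries, or whether a pre-existing event must worsen to be treatment-emergent.

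**The concern.** The recording rule and the classification rule were written separately and do not fit together. The first turns one clinical event into several dated records. The second then judges treatment emergence on dates or flags with nothing that refers back to the parent event. Two errors follow.

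- One on-treatment event that fluctuates is counted as several events.
- An event that began in screening or washout and improves on treatment yields a record with an on-treatment onset, which the date clause calls a TEAE although nothing emerged or worsened.

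The first error affects the descriptive event totals that will be read as the burden of AEs in each arm. The second can also put a patient into the TEAE incidence rows. In addition, the two clauses in SAP 8.8.2 give different answers when a site marks a continuation entry as prior, and the SAP does not say which one wins.

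**Working it through.** The documents give no figure for this point, so there is nothing to reproduce. The check applies Protocol 17.2 and SAP 8.8.2 to hypothetical episodes, with Day 1 as first application.

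**Step 1: counts per episode.** The third column takes each entry with onset on or after Day 1 as a TEAE and assumes that the site does not flag it as prior. The last two columns use one record per episode.

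| Episode | Entries | TEAEs as written | By first onset | First onset or worsening |
|---|---|---|---|---|
| A: pre-treatment moderate, mild from Day 10 | 2 | 1 | 0 | 0 |
| B: pre-treatment severe, moderate from Day 5, mild from Day 20 | 3 | 2 | 0 | 0 |
| C: mild from Day 8, moderate from Day 12, mild from Day 16 | 3 | 3 | 1 | 1 |
| D: pre-treatment mild, moderate from Day 10 | 2 | 1 | 0 | 1 |

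An on-treatment event with k grade changes counts k + 1 (C: 2 + 1 = 3). A pre-treatment event that only eases counts one TEAE per easing step (A: 1, B: 2) where the right number is 0.

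**Step 2: the flag.** Suppose the site marks the later entries of A, B and D as prior because the underlying event began earlier. The flag clause and the table footnotes then give 0, 0 and 0, while the date clause still gives 1, 2 and 1. The flag is right for A and B but drops the real worsening in D. Neither clause alone is right in all four cases.

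**Step 3: size of the event count.** With E on-treatment episodes, a share f changing grade and m changes each, entries = E(1 + f × m), so the ratio to the true count is 1 + f × m. Both f and m are assumptions.

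- Low: 1 + 0.10 × 1 = 1.10
- Middle: 1 + 0.20 × 1 = 1.20
- High: 1 + 0.30 × 2 = 1.60

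If there are also 10 pre-treatment episodes per 100 on-treatment ones, half of them easing on treatment and not flagged (assumed), the count goes from 110 + 10 × 0.5 × 1 = 115 to 160 + 10 × 0.5 × 2 = 170 per 100 true events.

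**Step 4: which outputs are reached.** Case C adds nothing to a once-per-patient count, because the patient already has that TEAE. Cases A and B can: a patient whose only AE is of this kind moves from no TEAE to one. The 1% threshold makes single patients matter. If all planned patients are in the safety population, 1/117 = 0.85% and 2/117 = 1.71%, so two vehicle patients bring a term into testing. In the active arm 2/234 = 0.85% and 3/234 = 1.28%, so three do.

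**The case against.** Much can be said for the plan, and several parts of it stand.

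- **Patient-level analyses are largely protected.** The once-per-patient rule keeps repeat entries out of the SOC and PT tables and the Fisher tests. A reader might infer that TEAE incidence and its tests are wrong in general; the documents do not support that. Only a reclassified pre-treatment event can reach them. It must be ongoing at first application, change grade afterwards, be left unflagged, and be the patient's only TEAE in that category. Screening may also fall on the same day as Baseline, so 35 days is a maximum.
- **Local reactions are mostly outside the AE data.** Protocol 16.1 and 16.2 make dryness, scaling, itching and burning/stinging AEs only if they lead to temporary discontinuation of product, withdrawal or a new medication.
- **Bias between arms is not shown.** A reader might infer that the arm that relieves washout complaints faster collects more false TEAEs. Pre-treatment events balance in expectation by randomisation, and the documents give no rate at which events ease or fluctuate in either arm. A differential is possible but is conjecture.
- **Not every count row is affected.** Outcome and action taken are recorded per AE, so a death or discontinuation would normally sit on one entry. The serious row is affected only if each entry is marked serious.
- **The flag may solve the easing case.** The listings show a field for occurrence before first application, but the CRF and its completion instructions are not in the documents. If sites use it that way, the conflict in Step 2 arises instead.
- **The programmer may collapse entries anyway.** Protocol 17.2 does distinguish an AE from its entries, so the table row could mean linked events. No derivation says so, and the result then depends on an unwritten choice.

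It is also fair that over-inclusion is the cautious direction for safety, that splitting captures case D, and that the listings let a reader join entries by hand. None of this supplies the missing rule.

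**Conclusion.** The concern holds for the event counts. As written, an on-treatment event with k grade changes contributes k + 1 to the number-of-TEAEs row. Under the assumption that 10% to 30% of events change grade once or twice, the total is 1.1 to 1.6 times the true number. That range rests wholly on assumed rates, and the documents allow no estimate.

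It holds conditionally for treatment emergence. A pre-treatment event that eases after first application becomes a TEAE unless the new entry is flagged as prior, and if it is flagged, the two clauses of SAP 8.8.2 contradict each other. The effect on patient-level incidence and the Fisher tests is confined to such reclassified events and is probably small.

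The point should be settled in the SAP because the remedy is cheap and the totals are otherwise hard to interpret. It does not bear on the efficacy conclusions.

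**What to change.** Add a derivation to SAP 8.8.2:

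1. Link consecutive entries of the same event: same term, with the next onset equal to or one day after the previous end date.
2. Classify the linked event by its first onset. Count a pre-existing event as a TEAE only if its severity after first application exceeds its severity before.
3. For a pre-existing event that worsens, report the onset of the worsening and the maximum severity after first application.
4. Base the number-of-events rows in Tables 14.3.1.2.1 and 14.3.1.3.1 on linked events.
5. State whether the date or the CRF flag governs when they disagree, and make the table footnotes match the text.
6. Keep the raw entries in the listings.

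The cost is SAP wording and a little programming. No data collection changes, and SAP Section 2 allows updates until the blind is broken.

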5.1. Synopsis

Safety Endpoints:	
• Adverse events (AEs), including serious adverse events (SAEs) occurring at any time during the trial.• Investigator Cutaneous Safety Assessment and Local Tolerability Assessments score at any time during the trial.
Safety:	The incidence of all adverse events reported during the study will be summarized by treatment group. Safety will be evaluated by comparing the nature, severity and frequency of their adverse event profiles. Safety variables include Investigator Cutaneous Safety Assessment score, treatment-emergent adverse events (AEs), SAEs, treatment related AEs, AEs leading to study discontinuation and concomitant medications

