19.6. Adverse Events

All adverse events occurring during the study will be recorded and classified on the basis of MedDRA terminology. Descriptions of AEs will include the date of onset, the date the AE ended, the severity of the AE, the relationship to study product, the action taken regarding study product usage, the action taken to treat the AE, and the outcome. All reported treatment-emergent AEs (TEAEs) will be summarized by the number of Patients reporting AEs, system organ class, severity, seriousness, and relationship to study product. TEAEs are those AEs with an onset on or after the date of the first study product application.

Adverse events will be summarized by treatment group and severity. Each patient will be counted only once within a system organ class or a preferred term by using the adverse events with the highest severity within each category.

Adverse events will be summarized by treatment group and relationship to study product. Each patient will be counted only once within a system organ class or a preferred term by using the adverse events with the greatest relationship within each category.

Comparisons among treatment groups will be made by tabulating the frequency of patients with one or more AEs (classified into MedDRA terms) during the study. The Fisher's Exact test will be used to compare the proportion of patients in each treatment group who report any adverse event at a significance level of 0.05. The specific system organ classes and preferred terms analyzed will be those that are reported by at least one percent of the patients in any treatment group.

All information pertaining to AEs noted during the study will be listed by patient, detailing verbatim given by the investigator, preferred term, system organ class, start date, stop date, severity, actions taken, and drug relatedness. The AE onset will also be shown relative (in number of days) to the day of initial dose of the randomized study product.

Serious adverse events (SAEs) will be tabulated by patient within treatment groups.

In addition, a list of patients who discontinued from the study and a list of patients who experienced SAEs will also be provided.

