8. STATISTICAL AND ANALYTICAL PLANS

8.1 General Methodology

All statistical processing will be performed using SAS® version 9.3 or later unless otherwise stated. Statistical significance will be based on two-tailed tests of the null hypothesis resulting in p-values of 0.05 or less. These methods are intended to analyze the results of the study.

The primary method of handling missing efficacy data will be based on estimation using the method of Markov Chain Monte Carlo (MCMC) imputation. This method provides robust estimation when the pattern of missingness is arbitrary. Additionally, the estimation will be done for each treatment group separately so that the pattern of missingness for one group does not influence the estimation of missing data for another group. Groups of complete datasets following the estimation will be concatenated to form analysis datasets for the comparative analyses and subsequent imputation result inference with SAS PROC MIANALYZE.

Descriptive statistics will also be derived from the multiply imputed datasets.

Additionally, a model-based multiple imputation process will be used as a sensitivity analysis to the MCMC imputation. Finally, the absolute change in lesion count will be analyzed using a repeated measures analysis of covariance (ANCOVA) for lesion count data and a repeated measures logistic regression model (generalized estimating equations) for the dichotomized IGA.

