Note: Treatment-emergent adverse events are those events that were not indicated as occurring prior to first application.
Related defined as “Definitely”, “Probably”, or “Possible”. Not Related defined as “Unlikely” or “Not related”.

SOURCE: USERNAME/SPONSOR/PROJECT/JOBNAME (DATE, TIME)

Table 14.3.1.3.2: Summary of Treatment-Emergent Serious Adverse Events by MedDRA System Organ Class and Preferred Term
(Safety Population)
(Page 1 of x)

System Organ Class ^a Preferred Term	E-BPO 5% Cream (N=xxx)	Vehicle Cream (N=xxx)	P-Value ^b
XXXXXXXXXXXXXXXXXXXXXXXXXXXX	xx (xx.x%)	xx (xx.x%)	x.xxx
XXXXXXXXXXXXXXXXXXXXXXXXXXXX	xx (xx.x%)	xx (xx.x%)	x.xxx

^a Counts reflect numbers of subjects reporting one or more adverse events that map to MedDRA. At each level of summarization (System Organ Class or Preferred Term) subjects are counted once.

^b P-value for the difference between treatment groups from a Fisher’s Exact test. The specific system organ classes and preferred terms analyzed will be those that are reported by at least one percent of the patients in any treatment group.

Note: MedDRA Version 21.0

Treatment-emergent adverse events are those events that were not indicated as occurring prior to first application.

SOURCE: USERNAME\SPONSOR\PROJECT\JOBNAME (DATE, TIME)

Table 14.3.1.3.3: Summary of Serious Treatment-Emergent Adverse Events by Severity
(Safety Population)
(Page 1 of x)

System Organ Class ^a Preferred Term	Severity	E-BPO 5% Cream (N=xxx)	Vehicle Cream (N=xxx)
XXXXXXXXXXXXXXXXXXXXXXXXXXXX	Severe	xx (xx.x%)	xx (xx.x%)
	Moderate	xx (xx.x%)	xx (xx.x%)
	Mild	xx (xx.x%)	xx (xx.x%)
XXXXXXXXXXXXXXXXXXXXXXXXXXXX	Severe	xx (xx.x%)	xx (xx.x%)
	Moderate	xx (xx.x%)	xx (xx.x%)
	Mild	xx (xx.x%)	xx (xx.x%)

^a Counts reflect numbers of subjects reporting one or more serious adverse events that map to MedDRA. At each level of summarization (System Organ Class or Preferred Term) subjects are counted once under the greatest reported severity.

Note: MedDRA Version 21.0.

Treatment-emergent adverse events are those events that were not indicated as occurring prior to first application.

SOURCE: USERNAME\SPONSOR\PROJECT\JOBNAME (DATE, TIME)

Table 14.3.1.3.4: Summary of Treatment-Emergent Serious Adverse Events by Relationship to Study Drug
(Safety Population)
(Page 1 of xx)

System Organ Class ^a Preferred Term	Relationship	E-BPO 5% Cream (N=xxx)	Vehicle Cream (N=xxx)
xxxxxxxxxxxxxxxxxxxxxxxxxxxxxxxx	Related	xx (xx.x%)	xx (xx.x%)

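### The only formal safety test is a Fisher p-value with no risk difference or interval, and at 234/117 it is insensitive to low-frequency adverse event excesses on active

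*SAP*

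**What the plan says.** Safety is part of the primary objective (Protocol 8; SAP 5), and the Protocol synopsis makes it comparative: "Safety will be evaluated by comparing the nature, severity and frequency of their adverse event profiles".

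SAP 8.8.2 first says that the arms are compared by tabulating how many patients had events. It then adds the formal test: Fisher's "Exact test will be used to compare the proportion of patients in each treatment group who report any AE". Its threshold is a "significance level of 0.05". The terms tested are "those that are reported by at least one percent of the patients in any treatment group". Protocol 19.6 has the same rule: "to compare the proportion of patients in each treatment group who report any adverse event at a significance level of 0.05". The test is two-sided under SAP 8.1: "Statistical significance will be based on two-tailed tests of the null hypothesis resulting in p-values of 0.05 or less".

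The p-value column appears in two shells. One is Table 14.3.1.2.2 (treatment-emergent events by class and term). The other is Table 14.3.1.3.2, "Summary of Treatment-Emergent Serious Adverse Events by MedDRA System Organ Class and Preferred Term". Footnote b of each applies the 1% limit. The overall rows for any treatment-emergent event and any serious one are in Tables 14.3.1.2.1 and 14.3.1.3.1, which show counts and percentages only. No safety section or shell plans a risk difference, a confidence interval or an upper bound.

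**The concern.** A comparative safety objective calls for a statement of how large an excess on active the data leave open. A p-value does not give that, least of all for infrequent terms. The 1% rule admits terms with as few as 3 active patients, well below the count at which the test can reach 0.05. A column of values above 0.05 beside such terms could be taken as reassurance when the test had little chance of reaching significance. With 2:1 allocation the test is also less sensitive to a low-frequency excess on active than to the same excess on vehicle.

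**Working it through.** **Inputs.** Planned arms of 234 and 117 (SAP 9), used in place of the safety population, whose size is not known in advance. Two-sided 0.05 (SAP 8.1 and 8.8.2). The 1% entry rule (SAP 8.8.2). The true event rates below are my assumptions; the documents give none.

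**The plan's own figures.** The plan gives no power for the safety test, only for efficacy, and those figures are sound. For IGA success at 53.3% against 20.0%, the continuity-corrected formula at 95% power and 2:1 gives 86/43, as stated. For lesions at 200/100, SE = √(6.70²/200 + 17.24²/100) = 1.788, and power = Φ(6.7/1.788 − 1.96) = Φ(1.787) = 96.3%, against the stated 95%.

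**Entry to the test.** 1% of 234 is 2.34, so 3 active patients qualify a term. 1% of 117 is 1.17, so 2 vehicle patients do.

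**Fisher p-values.** Given m events in total, the number on vehicle is hypergeometric: P(k) = C(117,k)·C(234,m−k)/C(351,m). The two-sided p adds every outcome no more probable than the one observed.

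- 8 active, 0 vehicle (m=8): P(0)=0.03747, P(6)=0.01617, P(7)=0.00220, P(8)=0.00013; p = 0.056.
- 9 active, 0 vehicle (m=9): P(0)=0.02469, P(7)=0.00673, P(8)=0.00079, P(9)=0.00004; p = 0.032.
- 0 active, 3 vehicle (m=3): P(3)=0.0364, and every other outcome is more probable; p = 0.036.

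| Vehicle events | Fewest active events for p≤0.05 | Active rate | p at that count (one fewer) |
|---|---|---|---|
| 0 | 9 | 3.8% | 0.032 (0.056) |
| 1 | 13 | 5.6% | 0.041 (0.068) |
| 2 | 16 | 6.8% | 0.042 (0.065) |
| 3 | 20 | 8.5% | 0.038 (0.059) |

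A term with 3 to 8 active patients and none on vehicle is therefore tested but cannot reach 0.05.

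**Stability.** Over safety sets from 200/100 to 240/111, 8 against 0 gives 0.055 to 0.060 and 0 against 3 gives 0.031 to 0.040. The threshold of 9 rises to 10 at 240/111 (9 against 0: 0.062; 10 against 0: 0.034).

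**Power.** This is the sum of binomial probabilities over all tables with p≤0.05 and the higher rate on the stated arm. For 3% against 0% on active it reduces to P(Bin(234, 0.03) ≥ 9) = 0.272. Mirrored onto vehicle it is P(Bin(117, 0.03) ≥ 3) = 0.685.

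| Assumed rates | Excess on active | Same excess on vehicle |
|---|---|---|
| 3% vs 0% | 27% | 69% |
| 5% vs 1% | 43% | 60% |
| 6% vs 2% | 34% | 46% |
| 10% vs 5% | 32% | 39% |
| 15% vs 5% | 82% | 85% |

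**What an interval would show.** Newcombe's interval combines the Wilson limits (l, u) of each arm: lower = d − √((p₁−l₁)² + (u₂−p₂)²), upper = d + √((u₁−p₁)² + (p₂−l₂)²). For 8/234, p₁=0.0342 with limits 0.0174 and 0.0660; for 0/117, limits 0 and 0.0318. So d = +3.4 points, lower = 0.0342 − √(0.0168² + 0.0318²) = −0.2 points, upper = 0.0342 + 0.0318 = +6.6 points. The p-value reports 0.056; the interval shows that an excess of up to about 6.6 points is not excluded.

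**The case against.** Several stronger readings are tempting, and the documents do not support them.

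- **That Fisher's test is the only between-arm safety comparison.** It is not. SAP 8.8.2 compares tabulated frequencies. Severity, relatedness, discontinuations, cutaneous safety, local tolerability, vital signs, physical findings and PGI-SE are all summarised by arm. It is the only formal safety test.
- **That real harms would be reported as no difference.** No section links p>0.05 to a safety conclusion, and the counts stand beside each p-value, so a reader can derive an interval. A risk of misreading is as far as the documents go.
- **That 8 against 3 measures the imbalance.** Much of that contrast is 2:1 allocation. As rates the thresholds are 3.8% and 2.6%. The mirrored power figures show that an asymmetry remains, and that it is smaller than the counts suggest.
- **That every serious event gets an uninformative p-value.** Footnote b of Table 14.3.1.3.2 withholds it from terms below 1% in both arms, and serious events are also listed by patient.

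Two further points stand. Dryness, scaling, itching and burning/stinging enter the adverse event tables only if they lead to interruption, withdrawal or new medication (Protocol 16.1 and 16.2), so most local reactions are judged from graded scores instead. And low power for single terms is unavoidable at this size; an interval does not raise it. It does make the remaining uncertainty visible, which the counts alone do not.

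**Conclusion.** The point holds as a cheap improvement. The formal safety analysis is significance testing without estimation. At the planned size, a term seen in up to 8 active patients and no vehicle patients cannot reach 0.05, and power against excesses of 3 to 5 points is about 27% to 43% under the rates assumed here. Those power figures depend on the assumed rates and on a safety population close to 234/117; the p-values for 8 against 0 and 0 against 3 do not depend on assumed rates and barely change over the sizes checked. They also depend on the two-sided test that the SAP specifies: the one-sided p for 8 against 0 is 0.037. What follows is that a non-significant p-value could be misread as comparable safety, and that the planned tables do not state what excess remains compatible with the data. It does not follow that the plan will draw a false safety conclusion, or that the p-value has to be removed.

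**What to change.** In SAP 8.8.2, add the risk difference (active minus vehicle) with a 95% confidence interval by one pre-specified method, for example Newcombe. Show it for each class and term reported by at least 1% in Tables 14.3.1.2.2 and 14.3.1.3.2, and for any treatment-emergent event and any serious one in Tables 14.3.1.2.1 and 14.3.1.3.1. The method should be named, because the choice can matter: for 8/234 against 0/117, Newcombe gives −0.2 to +6.6 points and Miettinen-Nurminen +0.2 to +6.6. State that the p-values are descriptive and that p>0.05 is not evidence of no difference. The Fisher p-value may stay beside the interval.

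The cost is a short SAP edit, extra columns in four shells and a little programming, with no new data. The intervals for rare terms will be visibly wide.
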